8.3.2 Exclusion Criteria

- 1. Other causes of liver disease (e.g., alcoholic liver disease, hepatitis B virus infection (see [Appendix 3](#)), chronic hepatitis C virus infection (see Appendix 3), autoimmune hepatitis, drug-induced hepatotoxicity, Wilson disease, α -1-antitrypsin deficiency, iron overload, and hemochromatosis)
- 2. Current or past history of HCC
- 3. Medical conditions
 - a) Past or current evidence of hepatic decompensation (e.g., ascites, variceal bleeding, hepatic encephalopathy and/or spontaneous bacterial peritonitis) or liver transplantation
 - b) Medical history of gastroesophageal varices, except if esophagogastroduodenoscopy [EGD] performed within 12 months prior to the Screening Period has shown \leq Grade 1 varices and without red wale signs, as assessed by the investigator)²⁶
 - c) Screening Fibroscan® elastography > 25 kPa (not applicable if EGD performed within 12 months prior to the Screening Period has shown \leq Grade 1 varices and without red wale signs, as assessed by the investigator)²⁶
 - d) Recent history (within 2 years prior to the biopsy used to determine eligibility) of drug or alcohol abuse as defined in the Diagnostic and Statistical Manual 5 (DSM-5), Diagnostic Criteria for Drug and Alcohol Abuse ([Appendix 4](#)) **OR** in the investigator's judgment, a pattern of excessive alcohol consumption ≥ 30 g/day (males) or ≥ 20 g/day (females). This alcohol consumption is equal to approximately 2 alcoholic drinks per day for males, and approximately 1.5 alcoholic drinks per day for females. One alcoholic drink is equal to 12 ounces (355 mL) of 5% alcohol by volume (ABV) beer, 5 ounces (148 mL) of 12% ABV wine, or 1.5 ounces (44.4 mL) of 40% ABV distilled spirits
 - e) Use of illicit intravenous drugs within 5 years prior to or during the Screening Period
 - f) A urine drug screen result positive for amphetamines, barbiturates, benzodiazepines, cannabinoids, cocaine, methadone, opiates, or phencyclidine during Screening, unless a prescribed drug accounts for the positive test
 - g) History of bariatric surgery or intestinal bypass surgery within the 5 years prior to informed consent or planned during the conduct of the study

- h) History of major surgery (i.e., surgery involving a risk to the life of the patient; specifically, an operation upon an organ within the cranium, chest, abdomen, or pelvic cavity) within 6 weeks prior to or during the Screening Period

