- b) ALT value $> 5 \times$ the upper limit of normal (ULN) as defined by the central laboratory
- c) AST value $> 5 \times$ ULN as defined by the central laboratory
- d) Total bilirubin > 1.5 mg/dL
- e) Serum albumin < 3.5 g/ dL
- f) Platelet count $< 100 \times 10^3/\mu\text{L}$
- g) International normalized ratio (INR) > 1.4 , unless due to therapeutic anticoagulation

[figure not shown]
- h) Fasting plasma glucose < 60 mg/dL (< 3.33 mmol/L) or > 350 mg/dL (> 19.43 mmol/L)
- i) Hemoglobin A1c ≥ 10%
- j) Fasting TGs > 500 mg/dL
- k) Estimated glomerular filtration rate (eGFR) < 30 mL/min/1.73 m² according to the Modification of Diet in Renal Disease equation
- l) Evidence of significant worsening of ALT, AST or bilirubin during the Screening Period, in the opinion of the investigator or medical monitor
- m) A centrally read DXA BMD T-Score of -2.5 or less at the femoral neck, total hip, or lumbar spine during Screening (exclusionary only if participant is 40 years of age or older)

[figure not shown]
6. Allergies and adverse drug reactions

- a) History of allergy to FGF21, PEG, or related compounds
- b) History of drug-induced liver injury (DILI)

7. Other exclusion criteria

- a) Prisoners or participants who are involuntarily incarcerated. **Note:** Under certain specific circumstances, a person who has been imprisoned may be included or permitted to continue as a participant. Strict conditions apply, and sponsor approval is required
- b) Participants who are compulsorily detained for treatment of either a psychiatric or physical (e.g., infectious disease) illness
- c) Any factor that, in the opinion of the investigator, would jeopardize the evaluation or safety of the participant or be associated with poor adherence to the protocol
- d) Participants who are incapable of completing study-related assessments (i.e., participant questionnaires) as they MUST be completed by the participant

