9.4.4 Exploratory Endpoints

- Quantitative measurements of fibrosis and fat on biopsy
 - Assessment of NASH CRN Fibrosis Score at Week 48
 - Assessment of Ishak Fibrosis Score at Week 48
 - Assessment of fibrosis using digital pathology at Week 48
 - Assessment of CPA at Week 48
 - Assessment of fat in stained tissue by morphometry at Week 48
 - Assessment of alpha smooth muscle actin at Week 48
- Assessment of NAS at Week 48
- Assessment of NASH using digital pathology at Week 48
- Hepatic fat fraction as measured using MRI-PDFF at Week 24 and Week 48
- Noninvasive measures of fibrosis and/or cirrhosis
 - Liver stiffness as determined by MRE at Week 24 and Week 48
 - Fibroscan elastography results at Week 48
 - Noninvasive scores of hepatic fibrosis (APRI, FIB-4, ELF, and NAFLD Fibrosis Score) at Week 24 and Week 48
- Metabolic assessments at Week 24 and Week 48
 - Physical assessments (body weight, waist circumference, and BMI)
 - Serum lipids (LDL, HDL, and TGs)
 - Plasma glucose
 - Plasma insulin
 - Hemoglobin A1c
- Child-Pugh Turcotte Score at Week 24 and Week 48
- MELD Score at each visit through Week 52/PTFU
- The event rate for any one (first occurrence) of the liver-related clinical outcome events described in Section 8.5.1.9 by Week 48
- Patient-reported outcomes at Week 24 and Week 48
 - EQ-5D-3L questionnaire
 - SF-36 questionnaire
 - CDLQ-NAFLD questionnaire
- Exploratory biomarkers
 - Transaminases
 - ALT normalization (ALT \leq ULN) at Week 24 and Week 48
 - AST normalization (AST \leq ULN) at Week 24 and Week 48

- ALT at each visit through Week 52/PTFU
- AST at each visit through Week 52/PTFU
- Change from Baseline (Day 1 predose) ALT levels at each visit through Week 52/PTFU Visit
- Change from Baseline (Day 1 predose) AST levels at each visit through Week 52/PTFU Visit
- o PRO-C3
 - Assessment of PRO-C3 levels at each visit through Week 52/PTFU
 - Change from Baseline (Day 1 predose) in PRO-C3 levels at each visit through Week 52/PTFU Visit
- o Assessment of adiponectin at each visit through Week 52/PTFU

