- Noninvasive scores of hepatic fibrosis (AST-Platelet Ratio Index (APRI), Fibrosis 4 (FIB-4), Enhanced Liver Fibrosis (ELF), and NAFLD Fibrosis Score) at Week 24 and Week 48
  - Absolute, percent change, and change from baseline
  - Proportion of participants in each ELF category by time point

Sponsor: Bristol-Myers Squibb

Protocol No.: MB130-069

- Metabolic assessments at Week 24 and Week 48
  - Physical assessments (body weight, waist circumference, and body mass index (BMI)) by time point
  - Serum lipids (low-density lipoprotein (LDL), high-density lipoprotein (HDL), and triglycerides (TGs))
    - Absolute and change from baseline
    - Abnormal postbaseline TG values according to thresholds identified in SAP [Section 4.3.5](#)
  - Plasma glucose, Plasma insulin, Hemoglobin A1c
    - Absolute and change from baseline
    - Abnormal postbaseline glucose values according to thresholds identified in SAP [Section 4.3.5](#)
- Child-Pugh Turcotte Score at Week 24 and Week 48
  - Proportion of participants in each Child-Pugh Turcotte class (A, B, C) by time point
  - Shift from baseline according to class (A, B, C)
- MELD Score at each visit through Week 52/PTFU
  - Absolute and change from baseline
- The event rate for any one (first occurrence) of the liver-related clinical outcome events by Week 48
  - Proportion of participants experiencing any of the events by Week 48
  - Proportion of participants experiencing each liver-related clinical outcome event by Week 48
- Patient-reported outcomes at Week 24 and Week 48
  - 3-Level EuroQol 5 Dimension (EQ-5D-3L) Questionnaire
    - Absolute and change from baseline in visual analog score and utility index
    - Proportion of participants in each 3-level dimension by time point
  - 36-Question Short Form Quality-of-Life (SF-36) Questionnaire
    - Absolute and change from baseline in continuous variables described in SAP [Section 8.0](#)
  - Chronic Liver Disease Questionnaire-Nonalcoholic Fatty Liver Disease (CDLQ-NAFLD)
    - Absolute and change from baseline in continuous variables described in SAP [Section 8.0](#)
- Exploratory biomarkers
  - Transaminases
    - ALT normalization (ALT  $\leq$  ULN) at Week 24 and Week 48
    - AST normalization (AST  $\leq$  ULN) at Week 24 and Week 48
    - ALT at each visit through Week 52/PTFU
    - AST at each visit through Week 52/PTFU
    - Change from Baseline (Day 1 predose) ALT levels at each visit through Week 52/PTFU Visit

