### 8.7 Child-Pugh Turcotte Score

The Child-Pugh Turcotte Score assesses the severity of cirrhosis and has been shown to be an accurate measure across a broad spectrum of liver disease. It employs numerical scores of 5 measures of liver disease: total bilirubin, serum albumin, International Normalized Ratio (INR), ascites, and encephalopathy. The sum of scores from each component is the final score (see below) used for determination of class.

Parameter	Classification	Score
Bilirubin (Total)	< 2 mg/dL (< 34.2 µmol/L)	+1
	2-3 mg/dL (34.2-51.3 µmol/L)	+2
	> 3 mg/dL (> 51.3 µmol/L)	+3
Albumin	> 3.5 g/dL (> 35 g/L)	+1
	2.8-3.5 g/dL (28-35 g/L)	+2
	< 2.8 g/dL (< 28 g/L)	+3
International Normalized Ratio	< 1.7	+1
	1.7-2.2	+2
	> 2.2	+3
Ascites	Absent	+1
	Slight	+2
	Moderate	+3
Encephalopathy	No encephalopathy	+1
	Grade 1-2	+2
	Grade 3-4	+3

Class A: 5 to 6 points (least severe liver disease)

Class B: 7 to 9 points (moderately severe liver disease)

Class C: 10 to 15 points (most severe liver disease)

Sponsor: Bristol-Myers Squibb

Protocol No.: MB130-069

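### The Child-Pugh Turcotte score is reported only by class, so a single one-point worsening from the usual 5-point start shows as A to A

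*SAP*

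**What the plan says.** Protocol 9.4.4 lists the exploratory endpoint as "Child-Pugh Turcotte Score at Week 24 and Week 48". Protocol 8.5.1.7 defines the score as the sum of five components, and Protocol Appendix 5 gives points only, with no classes.

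SAP 4.5 turns this into two categorical outputs: "Proportion of participants in each Child-Pugh Turcotte class (A, B, C) by time point" and "Shift from baseline according to class (A, B, C". SAP 8.7 treats the sum as a step on the way to class: "The sum of scores from each component is the final score (see below) used for determination of class". It sets the bands, among them "Class A: 5 to 6 points (least severe liver disease" and "Class B: 7 to 9 points (moderately severe liver disease".

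The next item in SAP 4.5, MELD, gets absolute values and change from baseline. ELF gets absolute values, change and percent change as well as categories.

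Protocol 8.3.2 excludes participants with "Serum albumin < 3.5 g/ dL", with total bilirubin above 1.5 mg/dL, with INR above 1.4 unless anticoagulation explains it, and with "Past or current evidence of hepatic decompensation".

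**The concern.** The entry criteria select people at or near the best possible score, and class A is two points wide. Someone who starts at 5 can lose a point on any one component and still be counted in the class where they began. The class shift table would then place a participant with new slight ascites in the same cell as one whose liver function did not change.

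What is at stake is how sensitive one exploratory display is. Child-Pugh is the only scheduled score in the plan that grades ascites and encephalopathy. MELD uses neither (Protocol 8.5.1.8), and it does not use albumin. In a population chosen for being compensated, the first step away from 5 is the earliest change this score can show.

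**Working it through.** **Inputs.** Component points and class bands are from SAP 8.7, entry limits from Protocol 8.3.2, planned outputs from SAP 4.5, and the MELD formula from SAP 8.13.

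**1. Reproduce the scale.** Five components score 1 to 3 each, so the minimum is 5 × 1 = 5 and the maximum 5 × 3 = 15. This matches the SAP bands: A 5-6, B 7-9, C 10-15.

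**2. Score the entry limits.**

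- Bilirubin is at most 1.5 mg/dL, below the 2 mg/dL cut: 1 point.
- Albumin is at least 3.5 g/dL. Above 3.5 scores 1; exactly 3.5 scores 2.
- INR is at most 1.4, below the 1.7 cut: 1 point. Under anticoagulation the limit is waived: 1.7-2.2 scores 2 and above 2.2 scores 3.
- Ascites and encephalopathy are absent: 1 point each.

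Sums are in the order bilirubin, albumin, INR, ascites, encephalopathy.

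| Participant at entry | Sum | Class |
|---|---|---|
| Not anticoagulated, albumin > 3.5 | 1+1+1+1+1 = 5 | A |
| Not anticoagulated, albumin exactly 3.5 | 1+2+1+1+1 = 6 | A |
| Anticoagulated, INR 1.7-2.2, albumin > 3.5 | 1+1+2+1+1 = 6 | A |
| Anticoagulated, INR 1.7-2.2, albumin exactly 3.5 | 1+2+2+1+1 = 7 | B |
| Anticoagulated, INR > 2.2, albumin > 3.5 | 1+1+3+1+1 = 7 | B |
| Anticoagulated, INR > 2.2, albumin exactly 3.5 | 1+2+3+1+1 = 8 | B |

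**3. Apply a worsening.**

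- From 5, one component up one point: 5 + 1 = 6, class A, for all five components.
- From 5, one component straight to its worst level (albumin below 2.8 g/dL, for example): 5 + 2 = 7, class B.
- From 5, two components up one point each: 5 + 1 + 1 = 7, class B.
- From 6, any component up one point: 6 + 1 = 7, class B.

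**4. Worked cases from a start of 5.** Albumin falling from 4.2 to 2.9 g/dL gives 6, A to A. Bilirubin rising from 0.8 to 2.9 mg/dL also gives 6, A to A. MELD would show the bilirubin case, because its bilirubin term rises by 3.78 × ln(2.9/0.8) = 3.78 × 1.288 ≈ 4.9 points. Albumin falling from 3.6 to 3.5 g/dL gives 6 as well, so one point can mean a fall of 0.1 g/dL or of 1.3 g/dL.

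**5. Where else each component is reported.**

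| Component | Other planned output |
|---|---|
| Albumin | Laboratory summaries, actual and change (SAP 6.2.4); flag below 2.8 g/dL (SAP 4.3.5), where the 3-point band begins |
| Bilirubin | Laboratory summaries; flag above 2 × ULN; MELD |
| INR | Laboratory summaries; MELD |
| Ascites | Liver-related event only if it needs medical treatment (SAP 8.8); otherwise possibly an adverse event (SAP 6.2.1) |
| Encephalopathy | Liver-related event only if hospitalised (SAP 8.8); otherwise possibly an adverse event (SAP 6.2.1) |

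Physical examination findings are listed, not summarised (SAP 6.2.3).

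**The case against.** The best defence is that little is lost. Three of the five components are laboratory values, summarised numerically by visit and arm, and bilirubin and INR also enter MELD. New ascites or encephalopathy of any grade fits the adverse event definition in Protocol Appendix 9, and treatment-emergent events are tabulated by preferred term and maximum severity. This stands. A reader might infer that an albumin fall to 2.9 g/dL, or new slight ascites, goes unreported in the trial; the documents do not support that. Only the Child-Pugh display fails to register it. What the defence does not supply is a graded summary of mild ascites and encephalopathy at Weeks 24 and 48.

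A second defence is that protocol and SAP do not conflict. Protocol 9.5.5 leaves the derivation of exploratory endpoints to the SAP, and class is derived from the score. That stands too: a reader might infer a contradiction, but this is a choice of summary.

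Third, SAP 6.4 says repeated measures models will be fitted to change from baseline for each exploratory endpoint. That could be read as covering the score. But SAP 4.5 defines this endpoint only by class, and the ANCOVA list in SAP 6.4 omits it, so a numeric analysis is not clearly specified. The table shells are a separate document (SAP Appendix 2) that was not available for this review.

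Finally, a count of one-point increases can pick up trivial crossings, because the albumin entry limit sits on the scoring cut. This is a fair caution about the remedy.

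**Conclusion.** The point holds as a minor one. For a participant starting at 5, the planned Child-Pugh outputs register none of the five possible single-component one-point worsenings. They do register a two-point worsening, and they register a one-point worsening for anyone starting at 6.

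This rests on three assumptions. The typical start of 5 is inferred from the entry limits; the documents do not give the number with albumin exactly 3.5 g/dL or on anticoagulants. Baseline is the last value before the Day 1 dose (SAP 8.1), so it can differ from the screening value that decided eligibility. The unseen table shells are assumed to follow SAP 4.5.

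Some stronger readings go too far. It is not true that any albumin fall leaves a participant in class A, since below 2.8 g/dL a 5-point participant reaches class B. It is not true that everyone starts in class A, since some anticoagulated entrants start at 7 or 8. Nothing in the documents shows that a one-point step is the likeliest change in 48 weeks, or that a table of A-to-A shifts would be taken as no effect on hepatic function. The primary and secondary analyses are not affected.

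**What to change.** In SAP 4.5, under Child-Pugh Turcotte Score, add by arm at Week 24 and Week 48:

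- the absolute numeric score and its change from baseline;
- the proportions with an increase of at least 1 point and of at least 2 points;
- counts in each level of the ascites and encephalopathy components.

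Keep the class proportions and class shift. State in SAP 6.4 whether the repeated measures model applies to the numeric score.

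The cost is SAP wording and one extra table; the components are already collected and summed to derive class. The drawback is that the 1-point count can include small albumin changes across the 3.5 g/dL cut. It should therefore be read alongside the 2-point count and the component counts. For those starting at 5, an increase of at least 2 points is the same as leaving class A, so the new information lies mainly in the 1-point and component counts.

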Participants will be stratified at randomization by country (Non-Japan/Japan). Participants in countries other than Japan will be stratified at randomization according to T2DM status (yes/no). Japanese participants will not be further stratified.

Randomized participants will receive their assigned double-blind study medication for a total of 48 weekly doses. The treatment will be administered by SC injection of 2 pre-filled syringes of study medication in the abdomen according to their assigned treatment arm (see Section 8.4.2). During the Double-Blind Treatment Period (Table 2 in Section 1), participants will be evaluated for safety and efficacy every 4 weeks (\pm 5 days) through Week 24 and every 8 weeks (\pm 5 days) after Week 24 through Week 48.

Participants will then return at Week 52 (\pm 5 days) for a PTFU Visit. Participants who discontinue study medication earlier than Week 48 will have an Early Termination (ET) Visit at the time of study medication discontinuation and will return for a PTFU Visit 4 weeks (\pm 5 days) after the ET Visit.

Participants will return 6 months (\pm 14 days) (1 month is defined as 4 calendar weeks) after the Week 52/PTFU Visit for DXA to assess BMD and for collection of samples for potential immunogenicity testing as well as serum and plasma biomarker samples (see Table 3 in Section 1). Participants at the Week 52/PTFU Visit may need to return at 9 months, 12 months, and 14 months (\pm 14 days) (1 month is defined as 4 calendar weeks) after the Week 52/PTFU Visit if required for immunogenicity testing, as described in Section 8.5.3.6 (see Table 3 in Section 1).

[figure not shown]
Figure 1 Study Design Schematic – Screening to Week 52/PTFU

ET = early termination; PTFU = Post-Treatment Follow-Up; QW = once weekly

^a For participants who discontinue study medication prematurely, liver biopsy will be performed at ET if the participant has completed at least Week 20. If a participant discontinues study participation prior to Week 20 they should consider having a liver biopsy at ET.

Figure 2 Study Schematic – Bone Mineral Density and Immunogenicity Follow-Up Visits After the Week 52/PTFU Visit (visit windows \pm 14 days) (1 month is defined as 4 calendar weeks)

DXA = dual-energy X-ray absorptiometry PTFU = Post-Treatment Follow-Up; QW = once weekly

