8.5.1.9 Liver-Related Clinical Outcome Events

Participants will be evaluated for the following liver-related clinical outcome events at each visit from Day 1 through Week 52/PTFU:

- All-cause mortality
- MELD Score ≥ 15 (with at least a 2-point increase from Baseline)
- Liver transplant
- Ascites requiring medical intervention
- Hospitalization (≥ 24 hours) for onset of variceal bleed
- Hospitalization (≥ 24 hours) for hepatic encephalopathy
- Hospitalization (≥ 24 hours) for spontaneous bacterial peritonitis
- HCC

If a participant experiences one of the above events, the investigator should contact the medical monitor within 48-72 hours to discuss further participation in the study.

Liver-related clinical outcome events will also be reported as AEs/SAEs, as applicable, as per Section [8.5.3.1](#) and [Appendix 9](#).

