8.5.3.1 Adverse Events

The definitions of an AE or SAE can be found in [Appendix 9](#).

AEs will be reported by the participant (or, when appropriate, by a caregiver, surrogate, or the participant's legally authorized representative).

The investigator and any designees are responsible for detecting, documenting, and reporting events that meet the definition of an AE or SAE and remain responsible for following up AEs that are serious, considered related to the study medication or the study, or that caused the participant to discontinue before completing the study.

For weight change (increase or decrease) to be considered an AE, the change should be 10% or more from Baseline that cannot be explained by lifestyle modifications alone.

Contacts for SAE reporting are specified in Appendix 9.

Time Period and Frequency for Collecting AE and SAE Information

Sections 5.6.1 and 5.6.2 in the IB represent the Reference Safety Information to determine expectedness of SAEs for expedited reporting.

The collection of nonserious AEs should begin at initiation of study medication and continue until the Week 52/PTFU Visit (Section 1)..

Following the participant's written consent to participate in the study, all SAEs, whether related or not related to study medication, must be collected, including those considered by the investigator to be related to study medication or protocol-specified procedures. All SAEs will be collected through the Week 52/PTFU Visit and will be reported as described in Appendix 9.

The investigator must report any SAE occurring after the Week 52/PTFU Visit that is believed to be related to study medication or a protocol-specified procedure.

- Medical occurrences that begin before the start of study medication but after obtaining informed consent will be recorded on the appropriate Section of the eCRF

- All SAEs will be recorded and reported to sponsor or designee within 24 hours, as indicated in [Appendix 9](#)
- The investigator will submit any updated SAE data to the sponsor or designee within 24 hours of this information being available

Investigators are not obligated to actively seek AEs or SAEs in former study participants. However, if the investigator learns of any SAE, including a death, at any time after a participant has been discharged from the study, and he/she considers the event reasonably related to the study medication or study participation, the investigator must promptly notify the sponsor.

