## 8.8 Liver-Related Clinical Outcome Events

Participants will be evaluated for the following liver-related clinical outcome events at each visit from Day 1 through Week 52/PTFU:

- All-cause mortality
- MELD Score  $\geq 15$  (with at least a 2-point increase from Baseline)
- Liver transplant
- Ascites requiring medical intervention
- Hospitalization ( $\geq 24$  hours) for onset of variceal bleed
- Hospitalization ( $\geq 24$  hours) for hepatic encephalopathy
- Hospitalization ( $\geq 24$  hours) for spontaneous bacterial peritonitis
- Hepatocellular Carcinoma (HCC)

Liver-related clinical outcome events will also be reported as AEs/SAEs, as applicable, as per ( Protocol Section 8.5.3.1 and [Appendix 9](#)).

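### The liver-related outcome event rate is planned as a plain proportion by Week 48, with no stated denominator and no allowance for the shorter follow-up of early stoppers

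*SAP*

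**What the plan says.** **Endpoint.** SAP 4.5 names it as "The event rate for any one (first occurrence) of the liver-related clinical outcome events by Week 48". Protocol 9.4.4 uses the same cut-off, "described in Section 8.5.1.9 by Week 48". SAP 4.5 then specifies two summaries: "Proportion of participants experiencing any of the events by Week 48", and the corresponding proportion for each event type.

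**Method.** SAP 6.4 assigns no specific method to this endpoint. It is absent from the list of dichotomous responses and from the ANCOVA list, and the repeated-measures model concerns changes from baseline. That leaves the general descriptive rules. SAP 6.4 allows either the mITT or the safety population for exploratory work. The denominator rule in SAP 6.5 does not define who is at risk; it lets denominators be adjusted, but only for by-visit summaries. SAP 6.4 has a missing-data rule for biopsy endpoints and none for outcome events.

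**Collection.** SAP 8.8 states: "Participants will be evaluated for the following liver-related clinical outcome events at each visit from Day 1 through Week 52/PTFU". Protocol 8.5.1.9 agrees. Under Protocol 8.1, those who stop medication before Week 48 "will have an Early Termination (ET) Visit at the time of study medication discontinuation and will return for a PTFU Visit 4 weeks" later. Protocol Table 3, which covers visits after that point, has no row for these events. Under Protocol 8.5.3.1, routine AE and SAE collection also ends at the post-treatment visit; afterwards only SAEs believed related to study medication or a protocol procedure must be reported. For people already discharged, "Investigators are not obligated to actively seek AEs or SAEs in former study participants".

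**The concern.** A proportion by Week 48 describes 48-week risk only if everyone in the denominator was watched for 48 weeks or had an event first. Someone who stops at Week 12 is last scheduled for evaluation at about Week 16. If that person stays in the denominator, the remaining 32 weeks are treated as known to be event-free. The result then depends on how many people stopped, and when, as well as on how many events occurred. With unequal stopping, the arm with more early stopping looks better.

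Stopping may also be related to liver status, since Protocol 8.3.9.1 lists abnormal liver tests among the reasons for discontinuing medication. The composite includes death, transplant, decompensation and liver cancer, and Protocol 6.2.1 says later trials will draw on all the efficacy and safety results of this study. A reader will therefore look at this row even though it is exploratory.

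**Working it through.** The documents give no figure for this endpoint to reproduce: no expected event rate and no expected discontinuation rate. The only design figure is power for the primary endpoint, which does not bear on the point. The stopping and event rates below are assumptions, shown as ranges.

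**Inputs from the documents.** Endpoint window 48 weeks (SAP 4.5, Protocol 9.4.4). Evaluation continues 4 weeks after early termination (Protocol 8.1). About 38 per arm and 155 in total (Protocol 6.2).

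**Assumptions.** Proportion stopping early d = 5% to 30%. True 48-week risk r = 2% to 10%. Constant hazard. Full mITT or safety denominator.

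**Step 1: person-time.** If early stoppers leave treatment at Week 24, their last evaluation is at Week 28. The observed fraction of 48-week person-time is 1 − d + d × (28/48).
- d = 10%: 0.900 + 0.058 = 0.958
- d = 20%: 0.800 + 0.117 = 0.917
- d = 30%: 0.700 + 0.175 = 0.875

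Ratio of 10% to 30% stopping: 0.958/0.875 = 1.095, or about 1.10.

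**Step 2: crude proportion against true risk.** Spread early stops uniformly over Weeks 0 to 48, with each stopper observed to 4 weeks after stopping. Mean time lost per stopper is 44²/(2 × 48) = 20.2 weeks. With h = −ln(1 − r)/48, the expected crude proportion is (1 − d) × r + d × m, where m is the average of 1 − exp(−h × min(t + 4, 48)) over stopping time t. At r = 5%, m is about 2.92%.

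| d | Crude proportion (true 5.00%) | Relative error | Expected events per 38 (true 1.90) |
|---|---|---|---|
| 5% | 4.90% | −2.1% | 1.86 |
| 10% | 4.79% | −4.2% | 1.82 |
| 20% | 4.58% | −8.3% | 1.74 |
| 30% | 4.38% | −12.5% | 1.66 |

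The relative error hardly changes with r: at d = 30% it is −12.6% for r = 2% and −12.3% for r = 10%. The largest absolute gap in the range is at r = 10%, d = 30%: 3.80 − 3.33 = 0.47 event per arm.

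**Step 3: unequal stopping, equal true risk of 5%.**
- 5% against 20% stopping: crude risk ratio 0.936
- 5% against 30%: 0.894
- 10% against 30%: 0.913

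The truth is 1.00 in each case. The last agrees with step 1 (0.875/0.958 = 0.913). In events, 10% against 30% is 1.82 − 1.66 = 0.16 per arm.

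**Step 4: Weeks 48 to 52.** Before dropout, extending the cut-off to Week 52 would add about 0.26, 0.63 or 1.22 expected events among 155 participants at r = 2%, 5% or 10%.

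**The case against.** **The denominator is inferred.** A reader might conclude that the SAP explicitly counts early stoppers as event-free. It does not. The full-population denominator is the natural reading, but the table shells are a separate document (SAP Appendix 2). This stands, and it limits the point to what follows if that denominator is used. The silence still matters, because two programmers could produce different percentages.

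**Nothing collected is thrown away.** A reader might infer that events in Weeks 48 to 52 are discarded, or that the SAP departs from the protocol. Neither is supported. The Week 48 cut-off is in Protocol 9.4.4 and matches the treatment period. SAP 8.8 says "Liver-related clinical outcome events will also be reported as AEs/SAEs, as applicable". The treatment-emergent window in SAP 8.4 runs to 30 days after the last dose, which for 48 weekly doses reaches about Week 51 (47 weeks + 30/7 = 51.3). SAP 6.2.1 lists all AEs, and MELD is summarised through Week 52. The AE route does not help early stoppers, though: for them AE collection ends at the same visit as liver-event evaluation.

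**These are not the only clinical outcomes.** Deaths, SAEs and Child-Pugh class are tabulated separately. This stands.

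**Kaplan-Meier has its own assumption.** Censoring at last evaluation assumes that stoppers carry the same later risk as those who remain, which is doubtful if stopping follows liver deterioration. This is a fair limit on the remedy, but it does not rescue the crude proportion, which assumes zero risk after loss. If stoppers are at higher risk, the crude figure is further from the truth.

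**Few events.** With one or two expected per arm at 2% to 5% risk, any estimate is imprecise. This stands, and it keeps the point minor.

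**Conclusion.** The point holds in a limited form. The plan turns a first-occurrence event rate into a plain proportion, stops scheduled event evaluation for early stoppers about 4 weeks after early termination, and states neither a denominator nor a rule for incomplete follow-up. On the likely denominator, the proportion is too low by about 2% to 13% in relative terms for 5% to 30% stopping, and more so in arms with more stopping. In absolute terms this is at most about 0.5 event per arm of 38.

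These sizes rest on assumed stopping and event rates, constant hazard, and attendance at the post-treatment visit; those who decline that visit lose more follow-up. Higher risk among stoppers would enlarge the error. The endpoint is exploratory and descriptive, and the primary analysis is untouched. This is a worthwhile low-cost improvement, not an error that changes the trial's conclusions.

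**What to change.** In SAP 4.5 and 6.4:
- Keep the crude count and percentage, and state the population, the denominator and how participants without evaluation to Week 48 are handled.
- Add time to first liver-related event by arm, with a Kaplan-Meier estimate at Week 48, censored at last evaluation and shown with numbers at risk. All-cause death is part of the composite, so it is not a competing event there; leave individual event types as counts.
- Add events per 100 person-years by arm, using all follow-up through Week 52/PTFU. This also brings in the Week 48 to 52 events without changing the protocol's endpoint.
- Note that Kaplan-Meier assumes non-informative censoring, and that discontinuation for abnormal liver tests may violate it.

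The cost is one extra table from event and visit dates in the existing data, with no new data collection. The added estimates will be imprecise with so few events and should be presented as descriptive.
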